1.3 Number of Subjects

In total 206 PFS events in the study would have 90% power to show statistically significant PFS at the 2-sided 5% level if the assumed true treatment effect were hazard ratio (HR) 0.62; this translates to a 8 month benefit in median PFS over 13 months on placebo (estimated from data reported by Alsop et al 2012) if PFS is exponentially distributed.

Approximately 344 patients will be recruited (2:1 ratio) so that data maturity for the PFS analysis is approximately 60%. When global enrolment closed on 14 November 2014, patients still in screening were permitted to be randomised and therefore a total of 391 patients were randomised as part of Global recruitment.

Assuming 18 months non-linear recruitment, 206 PFS events are expected to occur approximately 36 months after first subject in is enrolled in the study (FSI). At this time, an interim analysis of OS will also be performed.

PFS will be analysed when approximately 196 events have occurred or after the last patient randomised has had the opportunity to have been on the study for at least 36 months, whichever comes first. No further analyses of PFS are planned beyond this point unless requested by Health Authorities.

A further interim analysis of OS may be performed at approximately 206 events (~53% maturity of the 391 patients randomised). Assuming that the true OS treatment effect is 0.85 and this point estimate for the HR of 0.85 was observed, the 95% UCL for the HR would be 1.13. A final OS analysis may be performed at approximately 60% maturity (~235 events/391 patients who were randomised in SOLO1). Assuming that the true OS treatment effect is 0.85 and this point estimate for the HR of 0.85 was observed, the 95% UCL for the HR would be 1.11. Note that these estimates are based on the assumption that no confounding will occur. AstraZeneca considers there will be potential confounding of OS data due to availability of PARP inhibitors for BRCA mutated ovarian cancer patients during follow up in this study, which are likely to disproportionately affect OS in one arm of the study (placebo-treated patients).

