The scores will be derived in accordance with the FACT-O Scoring Manual. A number of items are negatively stated and need to be reversed by subtracting the response from "4". The scoring manual identifies that the following items need to be reversed prior to summarising: GP1-7, GE1, GE3-6, O1-3, C2, and B5. After reversing proper items, scores are summarised and multiplied by the number of items in the domain. For each subscale (domain), if less than 50% of the subscale items are missing, the subscale score will be divided by the number of non-missing items and multiplied by the total number of items on the subscale. If at least 50%

of the items are missing, that subscale also will be treated as missing. The reason for any missing assessment will be identified. If data are missing at random, the above techniques will be used. If there is evidence that the missing data are systematic, missing values will be handled to ensure that any possible bias is minimised. The TOI score ranges from 0-100 and the FACT-O from 0-152. For all Functional Assessment of Chronic Illness Therapy (FACIT) scales and symptom indices, a higher score indicates a higher HRQoL.

The actual change from baseline in TOI score will be derived for each visit where there is available data. For example; at visit X, the calculation will be (TOI score at visit X – baseline TOI score). Actual change from baseline for the individual FACT-O subscale scores will be calculated in a similar way. The baseline score is defined as last non-missing score prior to dosing with study treatment (olaparib or placebo). Any questionnaires completed on day 1 of dosing will be considered pre-dose.

A change of at least 10 points in TOI will be considered as a clinically relevant or a minimally important difference (Osobo et al 2005).

The threshold for a clinically important change is outlined below (Table 5):

Table 5 Health-Related Quality of Life

Score	Change from baseline	Visit response
TOI	≥+10	Improved
	≤-10 or "Subject too heavily affected by symptoms of disease under investigation" is answered as the reason for not completing HRQoL at visit.	Worsened
	Otherwise	No change

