Best overall TOI improvement (in absence of starting any subsequent cancer therapy) will be defined as a change from baseline in the TOI of + 10 points or more (Osoba et al 2005) sustained for at least 28 days, the denominator consisting of a subset of the FAS population who have baseline TOI. It will be derived as the best symptom improvement response the patient achieved, based on evaluable HRQoL data collected from randomisation up to the earliest of starting any subsequent cancer therapy or death. Therefore, at the conclusion of the trial, the following criteria, will be used to assign a best overall score response based on the individual visit responses (Table 6).

Table 6 Health-Related Quality of Life: Change rates - overall score

Best overall TOI score response	Criteria
Improved	Two visit responses of "improved" a minimum of 28 days apart without an intervening visit response of "worsened"
No change	Does not qualify for overall score response of "improved". Two visit responses of either "no change" or "improved and "no change" a minimum of 28 days apart without an intervening visit response of "worsened"
Worsened	Does not qualify for overall score response of "improved" A visit response of "worsened" without a subsequent response of "improved" or "no change" within 28 days.
Other	Does not qualify for one of the above.

In the calculation of the proportion of patients that have a response of Improved, No Change or Worsened, the denominator used in the calculation will use the number evaluable patients with a TOI score at baseline.

Summary measures of overall compliance and compliance over time will be derived for the FACT-O questionnaire. These will be based upon:

- Received forms = number of FACT-O forms received back plus the number not received back where the reason was 'Subject too heavily affected by symptoms of disease under investigation'.
- Expected forms = number of patients still under HRQoL follow-up at the specified assessment time excluding patients in countries with no available translation. For patients that have progressed, the latest of progression and safety follow-up will be used to assess whether the patient is still under HRQoL follow-up at the specified assessment time. Date of study discontinuation will be mapped to the nearest visit date to define the number of expected forms.

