4.2 Analysis Methods

The treatment comparison is olaparib 300 mg bd versus placebo.

All efficacy analyses will be performed on the ITT population. In addition, as a sensitivity to the main analyses of PFS, PFS2, OS, TDT, TFST and TSST, analyses of these endpoints will be performed in those patients whose gBRCAm status is confirmed by Myriad centrally. Each randomised patient will have one of either the Myriad BRACAnalysis CDx performed under Quality Systems Regulations (QSR) or the Myriad Integrated BRACAnalysis assay that is performed under Clinical Laboratory Improvement Amendments (CLIA).

Key efficacy (PFS, PFS2, OS, TDT, TFST and TSST) and safety estimates associated with patients whose tBRCAm status is confirmed by Foundation Medicine will also be reported as a separate subset.

Results of all statistical analysis will be presented using 95% confidence intervals and two-sided p-values.

The following table details which endpoints are to be subject to formal statistical analysis, together with pre-planned sensitivity analyses making clear which analysis is regarded as primary for that endpoint.

Table 7 Formal Statistical Analyses to be Conducted and Pre-Planned Sensitivity Analyses

Endpoints Analysed	Notes
PFS (Time from randomisation to first progression or death)	Primary analysis: stratified log-rank test using investigator data
	Key sensitivity analyses:
	 stratified log rank test using investigator data in randomised patients confirmed as gBRCA mutation positive by Myriad centrally
	 stratified log rank test using investigator data in randomised patients confirmed as tBRCA mutation positive by Foundation Medicine
	Additional sensitivity analyses:

Date 15 February 2022

Table 7 Formal Statistical Analyses to be Conducted and Pre-Planned Sensitivity Analyses

Endpoints Analysed	Notes
	1) Evaluation time bias analysis; stratified log- rank test using investigator data
	2) Attrition bias analysis (using alternative censoring rules); stratified log-rank test using investigator data
	3) Ascertainment bias analysis; stratified log-rank test using BICR data
	4) Deviation bias analysis (if meaningful to do); stratified log-rank test using investigator data
	5) Stratified log rank test using U and V statistics to calculate HR and CI based on investigator data
OS (Time from randomisation to death due to any cause)	Stratified log-rank test
	Key sensitivity analyses:

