During the randomised treatment phase, it is expected that olaparib will not cause harm to HRQoL, this will be demonstrated by comparing the Trial Outcome Index (TOI) best response rates (improved/no change/worsened) whilst on randomised treatment. A contingency table summarising the TOI best change rates will be provided and a CMH analysis including the randomisation stratification factor will be performed.

Date 15 February 2022

An AUC (Area Under the Curve) analysis will also be performed for TOI. For each patient, the AUC will be derived using the trapezoidal rule and including all available scheduled visits. Time-adjusted AUC will be calculated as AUC divided by time from baseline to last HRQoL visit where the patient provides data. The mean time-adjusted AUC will be analysed using analysis of variance (ANOVA) including using the same stratification factor as described for the primary analysis of PFS. Time-adjusted AUC summary statistics (mean, median, minimum, maximum, StD) per treatment arm will be presented. In addition, the analysis table will provide the estimated mean difference between treatment groups, 95% CI and p-value. This analysis will done using the first 24 months of data provided by a patient. For this analysis, for any patient who dies during the first 24 months, data for each question in the FACT-O from the time of death until 24 months will be set to 0. In addition, an analysis using all available data for each patient will be performed.

If deemed appropriate alternative methods may be used (e.g. piecewise linear modelling).

Descriptive statistics and graphs will be reported for the TOI by visits as well as change in these scores from baseline.

Total FACT-O and subscales scores

Descriptive statistics, by visit and change from baseline, will be reported for physical well-being (PWB), functional well-being (FWB) and the ovarian cancer subscale (Additional Concerns) domains. Descriptive statistics will also be provided for the individual questions that make up the additional concerns subscale.

Descriptive statistics, by visit and change from baseline, will also be reported for the emotional well being (EWB) and social well being (SWB) subscales, these two subscales do not form part of the TOI itself.

FACT-O questionnaire compliance (overall compliance and by visit compliance) will be summarised for each treatment group.

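### The SAP says absence of harm to quality of life on treatment will be demonstrated by a CMH comparison of TOI best response, but a difference test with no margin or criterion cannot show this

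*SAP*

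**What the plan says.** SAP section 4.2.9 sets out the purpose, for the period on study drug: "it is expected that olaparib will not cause harm to HRQoL, this will be demonstrated by comparing the Trial Outcome Index (TOI) best response rates". The response categories are improved, no change and worsened. The method is a contingency table of those categories, and "a CMH analysis including the randomisation stratification factor will be performed". Which CMH statistic is meant (general association, row mean score or correlation) is not stated.

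The categories come from SAP section 3.3.1: "A change of at least 10 points in TOI will be considered as a clinically relevant or a minimally important difference". Table 5 there applies plus or minus 10 points to each patient's change from baseline, and Table 6 combines the visit results into a best overall response. For the proportions, "the denominator used in the calculation will use the number evaluable patients with a TOI score at baseline". In that section the response is derived from data running from randomisation to subsequent cancer therapy or death. Section 4.2.9 speaks of the time on randomised treatment.

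SAP section 4.2 adds a general rule: "Results of all statistical analysis will be presented using 95% confidence intervals and two-sided p-values". Protocol section 12.2.3.6 plans only summary tables of TOI best change rates, with no test and no no-harm statement. SAP section 6 does not list the addition as a change from the protocol.

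**The concern.** CMH asks whether the arms differ. Failing to reject that null shows only that the data did not settle the question. To conclude no harm, one needs an estimate of the excess harm and an interval narrow enough to exclude an excess that matters. The section gives no between-arm margin, no success criterion, no assumed worsening rate and no named effect measure for worsening. The only stated route from the data to the conclusion is therefore the comparison itself, and the easiest reading of a p-value above 0.05 would be that no harm has been shown.

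At stake is a tolerability statement about a maintenance drug given to patients in response, many of whom have no evidence of disease. Such a statement should not gain strength from a small placebo arm or missing questionnaires, yet both make non-significance more likely.

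**Working it through.** **The plan's own figure.** There is none for this comparison. The power statement in SAP section 1.3 concerns PFS: 206 events, HR 0.62, 90% power, two-sided 5%, 2:1. The Schoenfeld formula gives (1.96 + 1.2816)² / [(2/3)(1/3)(ln 0.62)²] = 207, so that figure reproduces, but it says nothing about TOI.

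**Inputs.**
- Patients: "a total of 391 patients were randomised as part of Global recruitment" (SAP section 1.3). At 2:1 this is about 260 olaparib and 131 placebo. The split is derived, and it is an upper limit because only evaluable patients with a baseline TOI count.
- Level: two-sided 5%, from the general rule in SAP section 4.2.
- True harm: 10 percentage points more patients worsened on olaparib. This is illustrative and is not the 10 TOI points of section 3.3.1.
- Placebo worsening rate p: not given in either document, so a range of 5% to 40% is assumed.

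**Step 1: binary comparison, worsened or not.** With q = p + 0.10 and pooled rate m = (260q + 131p)/391:

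- SE0 = √[m(1−m)(1/260 + 1/131)]
- SE1 = √[q(1−q)/260 + p(1−p)/131]
- power = Φ[(0.10 − 1.96·SE0)/SE1]

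For p = 0.10: m = 0.1665, SE0 = 0.0399, SE1 = 0.0361, power = Φ(0.60) = 0.73, so 27% of trials miss the excess.

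| Placebo worsened | Missed, 260 v 131 | Missed, 208 v 105 (20% not evaluable, assumed) |
|---|---|---|
| 5% | 13% | 22% |
| 10% | 27% | 38% |
| 20% | 44% | 53% |
| 30% | 51% | 59% |
| 40% | 54% | 61% |

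An unpooled Wald test at 260 v 131 gives 21%, 40%, 49% and 53% for 10% to 40%. The pooled form is closer to CMH, which uses the null variance.

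**Step 2: the three-category test.** Stratified CMH tests were simulated under assumed 75/25 strata, with 15% improved in both arms and the same 10-point excess. Over placebo worsening of 10% to 40%, general association missed about 36% to 58% and row mean score about 62% to 75%.

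**Step 3: can improvement offset worsening?** Take placebo 15/65/20 and olaparib 25/45/30 (percent improved/no change/worsened), an assumed pattern with 10 points more of each extreme. Row mean score was significant in about 3% of simulated trials and general association in about 94%. Offsetting is thus real for one version of the test and not for the other, and the SAP does not say which applies.

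**Step 4: what an interval would show.** If both arms truly worsen at rate p, the 95% half-width for the difference is 1.96·√[p(1−p)(1/260 + 1/131)]: 4.6, 6.3, 8.4, 9.6 and 10.3 percentage points for p = 5%, 10%, 20%, 30% and 40%. An estimate of zero could still be compatible with an excess of roughly 5 to 10 points, which a bare p-value conceals.

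**The case against.** The case against is substantial on importance. The SAP never says that p > 0.05 will be read as no harm; a reader may infer that rule because no other is offered, but it is not written. The multiple testing procedure in SAP section 4.2.1 covers only PFS, PFS2 and OS. The primary FACT-O analysis is the MMRM, which reports a treatment difference with a 95% CI, as does the AUC analysis. The contingency table would show the worsening rates, and section 4.2 promises intervals in general. All this stands and limits the weight of the point. It does not supply an interval for worsening or tie any interval to the no-harm statement.

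Three stronger readings are tempting and are not supported.

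- A reader might infer that the 10-point TOI threshold plays no part in the conclusion. It does: it defines improved and worsened in Table 5. What is absent is a between-arm margin.
- A reader might infer that the existing MMRM interval could settle the matter, with no harm declared if its lower limit is above −10 points. This would be a poor rule. The MMRM averages 24 months from randomisation, and questionnaires continue after progression. Section 4.2.9 expects placebo patients to need chemotherapy earlier and quality of life to fall then, which could offset harm on treatment. Moreover, −10 is a threshold for one patient's change. If the averaged change had an SD of 15 (assumed), the half-width is 1.96·15·√(1/260 + 1/131) = 3.2, so an observed mean harm of up to about 6.8 points would pass. A true 5-point harm would pass in about 88% of trials (about 65% at SD 20, over 99% at SD 10).
- A reader might infer that any three-category CMH hides worsening behind improvement. That depends on the statistic chosen.

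**Conclusion.** The point holds. As written, the plan gives a difference test the task of demonstrating absence of harm, and no result of that test short of significant benefit bears on the claim. Even a benefit on a three-category scale need not exclude more worsening.

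The chance of missing 10 percentage points of excess worsening runs from about 13% at 5% placebo worsening to 54% at 40%, for a binary comparison with everyone evaluable. It is higher with missing data and was higher in the simulated three-category tests. These sizes rest on assumed worsening rates and an illustrative excess; the logical point needs neither. Because the analysis is supportive, carries no formal claim and sits beside an MMRM that reports an interval, importance is low to moderate.

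**What to change.** In SAP section 4.2.9:

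1. Say that the best response rates will be described, not that absence of harm will be demonstrated.
2. Report the difference between arms in the on-treatment proportion worsened, adjusted for the randomisation stratum, with its 95% CI.
3. Name the CMH statistic.
4. Reconcile the window with section 3.3.1: time on randomised treatment, or up to subsequent therapy or death.
5. Base any no-harm wording on the interval in item 2, not on a non-significant p-value. Any between-arm margin needs its own justification. Questionnaires were collected only up to the primary analysis cut-off, and SAP section 5 shows that the PFS analysis preceded this SAP, so label a margin added now as post hoc.
6. Do not use the 24-month MMRM difference against −10 TOI points as the no-harm rule.

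The cost is one more table line and some rewording; no new data are needed. The downside for the sponsor is that the statement becomes an estimate with stated uncertainty rather than a claim of demonstration.

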Patients known to have deleterious or suspected deleterious germline BRCA mutation/s (gBRCAm i.e., blood) prior to randomisation can enter the study based on this result. The result must be made available to AstraZeneca. In addition the patients must consent to provide 2 blood samples. One sample will be used for a confirmatory Myriad gBRCA test post randomisation using the current commercial Myriad BRCAnalysis® (gene sequencing and large rearrangement analysis), which will be paid for by AstraZeneca.

Patients with unknown BRCA status must consent to provide 2 blood samples for germline BRCA testing and follow all local ethical procedures for genetic testing. One sample will be used to test for BRCA mutations using the current commercial Myriad BRCAnalysis® test prior to study entry. The second is required for a bridging study to validate the companion diagnostic test for olaparib. These samples will be required for the study even if the patients are found not to have a BRCA mutation. When the result from the Myriad test indicates the

patient does have a deleterious or suspected deleterious BRCA mutation, the patient can be randomised into the study.

Patients will be randomised within 8 weeks after their last dose of chemotherapy (last dose is the day of the last infusion).

Randomisation will be stratified by:

• Response to first line platinum chemotherapy (in the opinion of the investigator, clinical complete response (CCR) or partial response (PR)).

Following randomisation patients in both treatment arms will attend clinic visits weekly for the first 4 weeks of treatment (Days 8, 15, 22 and 29). Patients will then attend clinic visits every 4 weeks whilst on study. Patients should continue to receive study treatment for up to two years or until objective radiological disease progression as per RECIST as assessed by the investigator and as long as in the investigator's opinion they are benefiting from treatment and they do not meet any other discontinuation criteria (see Section 5.8 of the Clinical Study Protocol (CSP)). Patients who continue to have evidence of disease that remains stable (i.e. no evidence of disease progression) at two years or those who have progressed may continue to receive study treatment if, in the opinion of the investigator, it is in the patient's best interest. However, if at two years the patient has no evidence of disease, study treatment should be discontinued.

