4.2.1 Multiplicity

In order to describe the nature of the benefits of olaparib maintenance treatment, PFS, PFS2, TFST, TSST, TDT change from baseline in TOI score and OS will be tested at a 2-sided significance level of 5%.

In addition to these planned analyses, which will be performed and reported in the CSR, in order to strongly control the type I error at 2.5% one-sided for key label claims, a multiple testing procedure (MTP) will also be employed across the primary endpoint (PFS) and key

secondary endpoints (PFS2 and OS). There is no requirement to adjust for multiplicity due to PFS interim analyses, since there are no planned interim PFS analyses with the opportunity to make an early claim of efficacy.

A hierarchical testing strategy will be employed where PFS is tested first using the full test mass (full test mass = alpha) and key secondary endpoints of PFS2 and OS will then be tested using a MTP with a recycling strategy (i.e., the MTP will recycle the test mass to the endpoint not yet rejected in the hierarchy outlined in Figure). The MTP is detailed below.

Figure 4 Multiple Testing Procedure

PFS2 will only be tested (with the test mass split between interim and final PFS2 analyses) if statistical significance is shown for PFS. OS will only be tested if statistical significance is shown for PFS2.

PFS2 will be tested at the time of the primary analyses of PFS and again when there are approximately 60% deaths. OS will be tested at the time of the primary analyses of PFS, again after approximately 206 events (approximately 53% maturity of the 391 patients randomised) and then again when there are approximately 60% deaths (~235 events out of 391 patients randomised). A proportion of alpha will be spent at this first analysis time point for both endpoints to control for multiple testing however different spending functions will be applied for each.

An interim analysis for PFS2 will be performed at the time of the PFS analysis Statistical significance will be declared at the interim analysis for PFS2 if the 1-sided p<0.0125.

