The MMRM model will include patient, treatment, visit (analysis) and treatment by visit interaction as explanatory variables, the baseline TOI score as a covariate along with the baseline TOI score by visit interaction. Treatment, visit and treatment by visit interaction will be fixed effects in the model; patient will be included as a random effect. Restricted maximum likelihood (REML) estimation will be used. An overall adjusted mean estimate will be derived that will estimate the average treatment effect over visits giving each visit equal weight. For this overall treatment comparison, adjusted mean estimates per treatment group and corresponding 95% CIs will be presented along with an estimate of the treatment difference, 95% CI and p-value. The treatment by visit interaction will remain in the model regardless of significance.

An unstructured covariance matrix will be used to model the within-subject error and the Kenward-Roger approximation will be used to estimate the degrees of freedom. The following provides sample code for implementing the MMRM analysis:

```
proc mixed data=TOI method = reml;
  class TRT VISIT SUBJECT;
  model TOISC = TRT VISIT TRT*VISIT TOIBL TOIBL*VISIT / s ddfm=kr;
  repeated VISIT / type=UN subject=SUBJECT;
  random intercept / subject= SUBJECT;
  lsmeans TRT / at means pdiff diff alpha=0.05 cl;
```

where TRT is the randomised treatment, VISIT is the visit, TOISC is the change from baseline in the TOI score, and TOIBL is the baseline TOI score.

For the estimation of trt*visit means an additional model will be run using all visits and the following Ismeans statement:

lsmeans TRT*VISIT / slice=VISIT pdiff diff alpha=0.05 cl;

If the fit of the unstructured covariance structure fails to converge, the following covariance structures will be tried in order until convergence is reached: toeplitz with heterogeneity, autoregressive with heterogeneity, toeplitz, and autoregressive. If there are still issues with the fit of the model or estimation of the treatment effects, SUBJECT will be treated as a fixed effect.

For each treatment and visit, the adjusted (least squares) mean estimates, corresponding 95% CIs, estimates of the treatment difference, corresponding 95% CIs and p-values will be presented.

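### The TOI area-under-the-curve comparison leaves out baseline TOI, so it is unbiased but less precise than it need be; adding the stratum to the TOI MMRM is a minor consistency fix

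*SAP*

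**What the plan says.** SAP 4.2.9 (Patient reported outcomes) plans three inferential TOI analyses with different adjustment.

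- **AUC.** A trapezoidal AUC of TOI is divided by the time from baseline to the patient's last HRQoL visit with data. Then: "The mean time-adjusted AUC will be analysed using analysis of variance (ANOVA) including using the same stratification factor". The sentence is slightly garbled, but it names no other covariate. As written, the outcome is TOI itself, not change from baseline. The table reports a mean difference, 95% CI and p-value. The main version uses the first 24 months and scores FACT-O items as 0 from death onward; a second version uses all available data.
- **MMRM** of change from baseline, designated the primary FACT-O analysis. The sample code has "model TOISC = TRT VISIT TRT*VISIT TOIBL TOIBL*VISIT / s ddfm=kr". Baseline TOI is in the model and the randomisation stratum is not. Protocol 12.2.3.6 also lists no stratum.
- **CMH** test of best TOI change, which includes the stratum.

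The only randomisation stratum is response to first-line platinum, complete or partial (SAP 1.2). SAP 3.3.1 defines baseline TOI as the last score before dosing. SAP 4.2.1 includes TOI in a list of endpoints each tested separately: "TDT change from baseline in TOI score and OS will be tested at a 2-sided significance level of 5" per cent. The multiple testing procedure itself covers only PFS, PFS2 and OS. SAP section 6 gives no reason for either omission.

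**The concern.** Baseline TOI is the obvious predictor of later TOI, and the SAP treats it so in the MMRM. When it is left out of the AUC model, stable differences between patients stay in the error term and a chance baseline imbalance stays in the estimate. The interval reflects that imbalance honestly, but it is wider than the available data require. What is at stake is the width of a reported interval and the p-value beside it.

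The MMRM has the reverse gap. Randomisation is blocked within the platinum-response stratum (Protocol 5.2.1), but the model does not carry that stratum, unlike the AUC and CMH analyses in the same section.

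**Working it through.** **1. The plan's own design figure.** The only power statement is for PFS: "In total 206 PFS events in the study would have 90% power to show statistically significant PFS at the 2-sided 5% level". The design effect is a hazard ratio of 0.62 (SAP 1.3). With 2:1 allocation, Schoenfeld's formula gives (1.960 + 1.282)² / [(2/3)(1/3)(ln 0.62)²] = 206.9, or 207 events; 206 events give 89.9% power. The figure reproduces. Nothing comparable exists for TOI: no SD, correlation or power is stated, so everything below is assumption-based.

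**2. AUC, equal correlation, no deaths.** The visits are baseline and weeks 4, 12, 24, …, 96 (SAP 4.2.9). Trapezoid weights divided by 96 weeks are 0.0208 (baseline), 0.0625, 0.1042, six of 0.125, and 0.0625; their squares sum to 0.1128. With unit variance and common correlation ρ:

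- cov(baseline, AUC) = ρ + (1 − ρ) × 0.0208
- var(AUC) = ρ + (1 − ρ) × 0.1128
- r = cov / √var
- SE reduction = 1 − √(1 − r²)
- equivalent sample factor = 1 / (1 − r²)

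| ρ | cov | var | r | SE reduction | sample factor |
|---|---|---|---|---|---|
| 0.4 | 0.4125 | 0.4677 | 0.60 | 20% | 1.57 |
| 0.5 | 0.5104 | 0.5564 | 0.68 | 27% | 1.88 |
| 0.6 | 0.6083 | 0.6451 | 0.76 | 35% | 2.35 |

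If change from baseline was intended as the AUC outcome, the covariate still helps. At ρ = 0.5 the unadjusted variance is 0.5564 + 1 − 2 × 0.5104 = 0.536, against 0.5564 × (1 − 0.468) = 0.296 with baseline in the model.

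**3. AUC, decaying correlation, no deaths.** With AR(1) correlation of 0.5 / 0.6 / 0.7 / 0.8 per 12 weeks and the same weights, r² = 0.11 / 0.16 / 0.24 / 0.37. The SE reduction is 6 / 8 / 13 / 20%.

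**4. AUC with deaths scored 0.** This was simulated with 391 patients, 2:1 blocks within stratum, mean TOI 75, SD 15, uniform death times, complete questionnaires otherwise, and AUC averaged over the full 96 weeks. ANCOVA/ANOVA SE ratios were:

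| ρ | no deaths | 5% deaths | 10% deaths |
|---|---|---|---|
| 0.4 | 0.80 | 0.91 | 0.94 |
| 0.6 | 0.66 | 0.82 | 0.88 |

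With deaths the SE falls by 6–18%. An assumed mean of 70 gives 7–20%. I carry forward about 6–19%, a sample factor of 1/0.94² = 1.13 to 1/0.81² = 1.52.

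**5. What this means for power.** With 391 patients at 2:1 and an assumed AUC SD of 15, a 5-point difference has 87% power unadjusted, 95% at r² = 0.25 and 97% at r² = 0.36. For 10 points, which SAP 3.3.1 calls clinically relevant, unadjusted power is at least 99.7% for SD up to 20 and 96% at SD 25.

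**6. MMRM with the stratum added.** This is approximated by complete-data ANCOVA on the post-baseline mean. Given baseline, the residual variance over nine visits is v = ρ + (1 − ρ)/9 − ρ². A stratum with share p and effect d (in SD units) adds p(1 − p)d² to the error if omitted, so the SE ratio is √[v / (v + p(1 − p)d²)]. Take ρ = 0.4, so v = 0.307, and assume p = 0.8:

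- d = 0.2: √(0.307/0.313) = 0.99
- d = 0.5: √(0.307/0.347) = 0.94

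Simulation agreed (0.989 and 0.939). The true sampling SD of the estimate did not change (0.828 with and without the stratum at ρ = 0.4, d = 0.2, no deaths), because randomisation already balances it. Only the reported SE was too large, with type I error of about 3–5% against a nominal 5%.

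**The case against.** The strongest objection is about size. A reader might take 20–35%, or 1.6 to 2.3 times the patients, as the loss. The documents do not support that for the planned 24-month variable: the AUC paragraph itself scores patients 0 after death, which adds variance that baseline cannot explain. Equal correlation across two years is also a favourable choice; the SAP plans an unstructured matrix with Toeplitz and autoregressive fallbacks. This stands and brings the estimate down. It does not reverse the direction: every scenario tried showed a gain.

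A reader might also infer that the MMRM wastes precision in the same way. It does not. It already has baseline TOI and baseline-by-visit, and adding the stratum leaves the true sampling variability unchanged. The documents do not say whether the stratum predicts TOI; if it does not, nothing is gained.

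A third inference is that the AUC and MMRM answer one question and could conflict merely through their covariates. They target different quantities. The MMRM averages change over visits with equal weight and has no death scoring; the AUC weights by time, includes the baseline point and scores death as 0. They could differ under identical covariates.

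Finally, timing. Protocol 6.5 says PRO collection has stopped, the SAP is dated 15 February 2022, and SAP section 5 places the PFS analysis before a March 2020 descriptive update. A model change now may be post hoc. That affects how the change is labelled, not whether ANCOVA is the better analysis.

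**Conclusion.** The point holds for the AUC at low severity. Omitting baseline TOI does not bias the comparison, but it costs precision at no compensating benefit. The plausible SE reduction from adding it is about 6–19% with 5–10% of patients scored 0 after death, and about 6–20% with decaying correlation and no deaths. It reaches 20–35% only with equal correlation of 0.4–0.6 and no deaths. The zero rule appears tied to the 24-month version, so the all-data version may lie nearer the no-death figures, subject to uneven follow-up. All of this rests on assumed correlations, SD, mean and death rate.

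The MMRM omission is an analyse-as-randomised inconsistency. It makes the reported SE about 1–6% too large if the stratum is prognostic for TOI, and has no effect otherwise.

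No primary or key secondary conclusion depends on either. TOI is outside the multiple testing procedure, the AUC supplements the MMRM, and under the assumed SDs the unadjusted analysis already has high power for a 10-point difference.

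**What to change.** In SAP 4.2.9, replace the ANOVA of time-adjusted AUC with an ANCOVA on treatment, platinum-response stratum and baseline TOI, for both the 24-month and all-data versions. If the ANOVA has already been reported, keep it as planned and document the ANCOVA as a supplementary analysis.

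As a consistency change, add platinum response as a fixed effect to the TOI MMRM text and sample code. Record it in SAP section 6, because Protocol 12.2.3.6 lists the model terms without it; the same supplementary labelling applies if the MMRM has been reported.

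The cost is two model terms and a line of documentation. It needs no new data, adds no patient burden and leaves the multiplicity scheme untouched.
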